- To investigate the safety (incidence and severity of adverse events) and tolerability (total dose and percentage of planned dose delivered in each cycle) of ITD combination therapy

Secondary

- Clinical benefit rate (CBR) defined as ORR + minimal response (MR)
- Duration of response (DOR)
- Progression free survival (PFS)
- To estimate the frequency of detection of minimal residual disease (MRD) within bone marrow aspirate samples by flow cytometry (using the Euroflow 8 colour panel) in patients assessed at suspected CR and determine its impact on PFS
- Change in global health status, as measured by the PRO instruments, EORTC QLQ-C30

Tertiary/Exploratory

- Minimal residual disease (MRD) assessment via centralised next-generation (EuroFlow) flow cytometry (MFC) and correlation with serological measures of disease burden (SPEP, FreeLite). MFC to be undertaken at suspected CR.
- Purification and storage of CD138 positive MM cells at base-line for potential exploratory biomarker studies
- Isolation of circulating DNA, RNA and MiRNA at base line, 3 and 6 months post trial commencement and at relapse for potential exploratory biomarker, MRD studies and exploratory mutational analyses baseline vs. relapse.

Overview of Study Design:

A prospective, single arm, multi-centre, phase 2 trial of the addition of ixazomib to a thalidomide/dexamethasone (TD) backbone. The primary objective is to determine ORR and the safety and tolerability of the combination.

Study Population:

Adult patients with relapsed/refractory multiple myeloma as per international myeloma working group (IMWG) criteria who have received 1-3 lines of previous therapy.

Duration of Study: Individual patients will remain on study until disease progression, unacceptable toxicity or consent withdrawal, whichever occurs first.

SCHEDULE OF EVENTS

Schedule of Events							
	Screening ^a	For each 28 day cycle		Day 1 of cycles 3 and 6	At serological CR	EOT ^c	Follow Up ^j
		Day 1	Day 15 ^b				
Study Procedures	-28 to -1						
Informed Consent	X						
Inclusion/Exclusion Criteria	X						
Demographics	X						
Medical history	X						
MM stage at diagnosis and prior MM therapies	X						
MM diagnostic karyotype and FISH if available	X						
Symptom-directed Physical Examination	X	X					X
Neurological Assessment	X	X				X	
ECOG	X	X					
Vital Signs	X	X	X				
Pregnancy Test ^d	X	X				X	
12-lead ECG	X						
FBE	X	X	X			X	
Biochemistry	X	X	X			X	
QOL assessment ^e	X	X				X	
Health Care Utilisation	X	X				X	

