5. STUDY POPULATION

5.1 Inclusion Criteria

Each patient must meet all of the following inclusion criteria to be enrolled in the study:

1. Male or female patients 18 years or older.
2. Voluntary written consent must be given before performance of any study related procedure not part of standard medical care, with the understanding that consent may be withdrawn by the patient at any time without prejudice to future medical care.

3. Female patients who:

- Are postmenopausal for at least 1 year before the screening visit, OR
- Are surgically sterile, OR
- If they are of childbearing potential, agree to practice 2 effective methods of contraception, at the same time, from the time of signing the informed consent form through 90 days after the last dose of study drug, OR
- Agree to practice true abstinence when this is in line with the preferred and usual lifestyle of the subject. (Periodic abstinence [eg, calendar, ovulation, symptothermal, post-ovulation methods] and withdrawal are not acceptable methods of contraception.)

Male patients, even if surgically sterilized (ie, status post-vasectomy), must agree to one of the following:

- Agree to practice effective barrier contraception during the entire study treatment period and through 90 days after the last dose of study drug, OR
- Agree to practice true abstinence when this is in line with the preferred and usual lifestyle of the subject. (Periodic abstinence (eg, calendar, ovulation, symptothermal, post-ovulation methods] and withdrawal are not acceptable methods of contraception.)

4. Patients must have a diagnosis of a relapsed/refractory multiple myeloma and have had between 1-3 prior therapies

5. Eastern Cooperative Oncology Group (ECOG) performance status 0, 1, or 2 (See appendix 11.1).

6. Patients must meet the following clinical laboratory criteria:

- Absolute neutrophil count (ANC) $\geq 1,000/\text{mm}^3$ and platelet count $\geq 75,000/\text{mm}^3$. Platelet transfusions to help patients meet eligibility criteria are not allowed within 3 days before study enrollment.
- Total bilirubin $\leq 1.5 \times$ the upper limit of the normal range (ULN).
- Alanine aminotransferase (ALT) and aspartate aminotransferase (AST) $\leq 3 \times$ ULN.
- Calculated creatinine clearance ≥ 30 mL/min (see Appendix 11.3).

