7. STATISTICAL AND QUANTITATIVE ANALYSES

7.1 Statistical Methods

The primary efficacy and safety analyses will be conducted after all patients, who are still receiving ITD combination therapy have completed 4 cycles of therapy. The additional data for patients continuing to

receive study treatment beyond this time, as allowed by the protocol, will be summarized in a final report once all patients remaining on study have completed 1 year of follow-up.

The primary efficacy analysis will be an intention-to-treat analysis conducted on the Full Analysis Set (FAS) which comprises all patients registered on the study. A sensitivity analysis of the primary efficacy endpoint will also be conducted on the Per-Protocol Set (PPS) which consists of a subset of patients in the FAS who have been compliant with the requirements of the protocol, i.e. patients without a major protocol deviation. Major protocol deviations include, but are not limited to, incomplete documentation of response status at registration, a response status of MR or better at registration, and, other anti-neoplastic therapy administered after registration on the study. Major protocol deviations will be documented, and the PPS will be determined, prior to locking the database for the primary efficacy analysis. The primary safety analysis will be conducted on the Safety Set which consists of the subset of patients in the FAS who received at least one dose of ixazomib.

Demographic and other baseline data collected at registration will be summarized descriptively for the FAS. Categorical data will be presented as frequencies and percentages. For continuous data, means, standard deviations, medians, 25th and 75th percentiles, minima and maxima will be presented.

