7.1.4 Procedures for Handling Missing, Unused, and Spurious Data

Patients without re-staging information for any reason and who are not known to have achieved at least a PR while on ITD therapy will be deemed to have not met the primary efficacy endpoint. Time to event data will be censored at the study censor date (see below) except for patients deemed lost to follow-up – their time to event data will be censored at the earlier of the study censor date and the date of last assessment. Missing quality of life data will, in linear mixed model analyses, be assumed to be missing at random, but if the missingness is due to death or withdrawal from the study due to unacceptable toxicity or progression, the missing measures will be imputed and the patient deemed to have “zero” global quality of life from the date of withdrawal from the study.

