7.1.6 Efficacy Analysis

The primary efficacy objective is to determine the overall response rate to treatment with ITD combination therapy in RRMM patients. Overall response is defined as achievement of a PR or better

(PR, VGPR, CR or sCR) as defined by the IMWG criteria (Appendix 4). The overall response rate (ORR) will be calculated as the number of patients who have experienced at least a partial response, divided by the number of patients registered on the trial. Patients who withdraw from the study prior to re-staging, or who are lost to follow-up before re-staging and are not known to have achieved at least a PR, or whose re-staging information is missing for any reason, will be considered to have not met the primary efficacy endpoint.

The primary efficacy analysis will be based on the calculation of the observed ORR and its posterior probability distribution. Evidence of efficacy of the ITD combination therapy will be based on two PoC criteria:

1. Observed ORR \geq 60%
2. Posterior probability that the true ORR exceeds 45% is $>$ 90% (given the observed data)

In addition, the percentiles of the posterior probability distribution for ORR, in particular the 95% uncertainty interval, defined by the 2.5 and 97.5 percentiles and also the posterior probability that the true ORR exceeds 45%, will be reported. The analysis will use a minimally informative prior distribution for the ORR, namely, Beta($a=0.86805$, $b=1$) for which the median ORR is 45% and the amount of prior information is equivalent to approximately 1.87 ($=a+b$) patients.

If an interim analysis of ORR is required for any reason (e.g. a review of efficacy by the TMC or sponsor), the posterior probability distribution will be updated, using the minimally informative prior distribution and the accumulated data, and reported as appropriate.

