11.4 IMWG Response Criteria

Adapted from International Myeloma Working Group uniform response criteria¹ and Kyle and Rajkumar².

Stringent Complete Response (sCR)

CR as defined below plus

Normal FLC ratio and

Absence of clonal cells in bone marrow by immunohistochemistry or immunofluorescence¹

Complete Response² (CR)

Negative immunofixation on the serum and urine and

Disappearance of any soft tissue plasmacytomas and

<5% plasma cells in bone marrow³

Very Good Partial Response (VGPR)

Serum and urine M-protein detectable by immunofixation but not on electrophoresis or 90% reduction in serum M-protein plus urine M-protein <100mg per 24 hour

Partial Response⁴ (PR)

≥ 50% reduction of serum M-protein and reduction in 24 hour urinary M protein by ≥ 90% or to <200mg per 24 hour

If the serum and urine M protein are unmeasurable⁵, a ≥ 50% decrease in the difference between involved and uninvolved FLC levels is required in place of the M-protein criteria. If serum and urine M-protein are

¹ Confirmation with repeat bone marrow biopsy not needed

² Note clarification to IMWG criteria for coding CR and VGPR in patients in whom the only measurable disease is by serum FLC levels: CR in such patient is defined as a normal FLC ratio of 0.26-1.65 in addition to CR criteria listed above. VGPR in such patients is defined as a >90% decrease in the difference between involved and uninvolved FLC levels.

³ Confirmation with repeat bone marrow biopsy not needed

⁴ Confirmation with repeat bone marrow biopsy not needed

⁵ In order to apply definition, patient must have measurable disease defined by at least one of the following:

- Serum M-protein ≥ 1g/dl
- Urine M-protein ≥200mg/24hour
- Serum FLC assay : Involved FLC level ≥ 10mg/dl provided serum FLC ratio is abnormal Bone marrow plasma cells ≥ 30%

unmeasurable, and serum free light assay is also unmeasurable, $\geq 50\%$ reduction in plasma cells is required in place of M-protein, provided baseline bone marrow plasma cell percentage was $\geq 30\%$

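### Section 5 does not require measurable disease or exclude patients already in response, although the response criteria presuppose the first and Section 7.1 treats the second as a major deviation

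*Protocol*

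**What the plan says.** **Entry.** Inclusion criterion 4 (Protocol 5.1) reads "Patients must have a diagnosis of a relapsed/refractory multiple myeloma and have had between 1-3 prior therapies". None of the other inclusion criteria, and none of the 20 exclusion criteria in 5.2, mentions measurable disease, current progression or an existing response. The Protocol Summary describes the population as "Adult patients with relapsed/refractory multiple myeloma as per international myeloma working group (IMWG) criteria". It is silent on measurability, and criterion 4 does not repeat its reference to IMWG criteria.

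**Response.** Footnote 5 in Appendix 11.4, attached to the partial-response (PR) paragraph, says "In order to apply definition, patient must have measurable disease defined by at least one of the following". It then gives four alternatives: serum M-protein of at least 1 g/dl, urine M-protein of at least 200 mg/24 h, involved free light chain (FLC) of at least 10 mg/dl with an abnormal ratio, or marrow plasma cells of at least 30%.

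**Analysis.** The Full Analysis Set (FAS) is the primary set, "which comprises all patients registered on the study" (7.1). Section 7.1.6 defines overall response as PR or better, with the count of responders "divided by the number of patients registered on the trial". Patients who lack re-staging information and are not known to have reached PR "will be deemed to have not met the primary efficacy endpoint" (7.1.4). The major deviations listed in 7.1 include "incomplete documentation of response status at registration, a response status of MR or better at registration". They remove a patient only from the Per-Protocol Set, which serves a sensitivity analysis.

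**The concern.** The endpoint has a precondition that the entry criteria never impose. A patient can satisfy every line of Section 5 and still have no baseline from which a PR can be measured, or be a major protocol deviation on the day of registration. Both kinds of patient stay in the primary denominator.

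The success rule leaves little room for this. The 60% observed-rate criterion means 27 responders among 45, and the sample size has no allowance for patients who cannot be scored. If unmeasurable patients enter, the observed ORR tends to fall. If patients already in response enter and their earlier response is credited to the study regimen, it tends to rise. Either way the comparison with 45% and 60% is no longer a clean reading of the combination's activity.

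**Working it through.** **Inputs.** n = 45; success needs an observed ORR of at least 60% and a posterior probability above 90% that the true ORR exceeds 45%; prior Beta(0.86805, 1); stated power 0.80 at a true ORR of 65% (Protocol 7.1.1 and 7.1.6). Section 7.1.1 allows exactly 90% for the posterior; this does not change the cut-off.

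**Step 1: the cut-off.** 0.60 × 45 = 27 responders. The posterior probability that the true ORR exceeds 45%, from Beta(0.86805 + x, 1 + 45 − x), is 0.866 at x = 24, 0.919 at x = 25 and 0.977 at x = 27. The posterior criterion is already met at 25, so the 60% criterion decides.

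**Step 2: the plan's own figure.** P(X ≥ 27) with X ~ Bin(45, 0.65) is 0.806, which agrees with the stated 0.80. At a true ORR of 45% the same probability is 0.031.

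**Step 3: unscorable patients (illustration).** Two assumptions are added that the protocol does not make: 65% is the ORR among scorable patients, and k of the 45 registered patients cannot be scored and count as non-responders. Power is then P(X ≥ 27) with X ~ Bin(45 − k, 0.65).

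| k | share of 45 | power |
|---|---|---|
| 0 | 0% | 0.806 |
| 1 | 2.2% | 0.749 |
| 2 | 4.4% | 0.683 |
| 3 | 6.7% | 0.608 |
| 4 | 8.9% | 0.526 |
| 5 | 11.1% | 0.441 |

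Under the same assumptions, an unscorable share above 1 − 0.60/0.65 = 7.7% puts the true ORR over all registered patients below 60%. Because criterion 1 is a fixed observed rate, more patients could not then restore 0.80.

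**Step 4: patients already in response (illustration).** Suppose instead that k registered patients are in PR or better at entry and all count as responders. Efficacy is then declared if the other 45 − k patients give at least 27 − k responses.

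| k | true ORR 45% in the others | true ORR 65% in the others |
|---|---|---|
| 0 | 0.031 | 0.806 |
| 3 | P(Bin(42, 0.45) ≥ 24) = 0.077 | P(Bin(42, 0.65) ≥ 24) = 0.889 |

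The two mechanisms pull in opposite directions, and the protocol gives no frequency for either.

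**The case against.** The best reply is that the power calculation is correct as written. Section 7.1.6 defines ORR over all registered patients, so the 65% in 7.1.1 can be read as a rate that already includes anyone who cannot be scored. That stands. A reader might infer from Step 3 that the stated 0.80 is wrong, or is lost by design. The documents do not support that, because the loss needs both added assumptions.

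A reader might also infer that response can be scored only in measurable disease, so that an unmeasurable patient is automatically a failure. That goes beyond the text. Footnote 5 hangs on the PR paragraph, and the complete-response text (negative immunofixation, no soft-tissue plasmacytoma, under 5% marrow plasma cells) states no such condition. Sections 7.1.4 and 7.1.6 fail patients for missing re-staging, withdrawal or loss to follow-up, and do not name unmeasurable disease. Non-responder is the probable outcome, not a stated rule.

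Three further points have weight:

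- Footnote 5 is broad, and any one of its four criteria is enough, so few relapsed patients may fail all of them.
- The Summary's reference to IMWG criteria suggests progression, and the entry "a response status of MR or better at registration" in the deviation list shows that such patients were not meant to enter. But a deviation label acts after registration and affects only the sensitivity analysis.
- Incomplete baseline documentation is a failure of conduct rather than a gap in eligibility, since the relevant tests are scheduled at screening. It is not part of this point.

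**Conclusion.** The point holds as a misalignment between Section 5.1 on one side and Appendix 11.4 and Section 7.1 on the other. As written, the plan can admit patients whose primary endpoint cannot be scored properly, and it keeps them in the primary denominator.

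The missing criterion is plain from the text. The size of its effect is not. The power figures rest on reading 65% as the rate in scorable patients and on an assumed k; the inflation figures rest on every patient already in response being counted as a responder. With k = 0 or 1 in Step 3, power is 0.81 or 0.75, and nothing in the documents makes k = 4 or 5 more likely than that. It would also be wrong to describe the effect as dilution alone, since patients already in response could raise the ORR.

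This is a cheap improvement to the protocol, not an error in its sample-size calculation.

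**What to change.** Add to Section 5.1 a criterion requiring, at registration, (a) measurable disease by at least one of the four alternatives in footnote 5 of Appendix 11.4 and (b) relapse or progression by IMWG criteria, so that the patient is not in minimal response or better. Confirm both before registration from the serum and urine electrophoresis, FLC assay and bone marrow examination already in the screening column of the Schedule of Events. Keep the FAS denominator at all registered patients, so that the intention-to-treat reading of the ORR is preserved.

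The cost is one eligibility amendment and no new tests. The downside is slightly narrower eligibility and possibly slower accrual.

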5.2 Exclusion Criteria

Patients meeting any of the following exclusion criteria are not to be enrolled in the study:

1. Patients with known thalidomide refractory disease or thalidomide intolerance.
2. Female patients who are lactating or have a positive serum pregnancy test during the screening period.
3. Failure to have fully recovered (ie, \leq Grade 1 toxicity) from the reversible effects of prior chemotherapy.
4. Major surgery within 14 days before enrollment.
5. Radiotherapy within 14 days before enrollment. If the involved field is small, 7 days will be considered a sufficient interval between treatment and administration of the combination of ixazomib, thalidomide and dexamethasone.
6. Central nervous system involvement with the disease under study (multiple myeloma).
7. Infection requiring systemic antibiotic therapy or other serious infection within 14 days before study enrollment.
8. Evidence of current uncontrolled cardiovascular conditions, including uncontrolled hypertension, uncontrolled cardiac arrhythmias, symptomatic congestive heart failure, unstable angina, or myocardial infarction within the past 6 months.
9. Systemic treatment, within 14 days before the first dose of ixazomib, with strong CYP3A inducers (rifampin, rifapentine, rifabutin, carbamazepine, phenytoin, phenobarbital), or use of Ginkgo biloba or St. John's wort.
10. Ongoing or active systemic infection, active hepatitis B or C virus infection, or known human immunodeficiency virus (HIV) positive.
11. Any serious medical or psychiatric illness that could, in the investigator's opinion, potentially interfere with the completion of treatment according to this protocol.
12. Known allergy/intolerance to any of the study medications, their analogues, or excipients in the various formulations of any agent.

13. Known GI disease or GI procedure that could interfere with the oral absorption or tolerance of ixazomib, thalidomide and/or dexamethasone including difficulty swallowing.
14. Diagnosed or treated for another malignancy within 2 years before study enrollment or previously diagnosed with another malignancy and have any evidence of residual disease. Patients with nonmelanoma skin cancer or carcinoma in situ of any type are not excluded if they have undergone complete resection.
15. Patient has \geq Grade 2 peripheral neuropathy, or Grade 1 with pain on clinical examination during the screening period.
16. Participation in other clinical trials, including those with other investigational agents not included in this trial, within 30 days of the start of this trial and throughout the duration of this trial.
17. Patients that have previously been treated with ixazomib, or participated in a study with ixazomib whether treated with ixazomib or not.
18. Patients who are either contraindicated or unwilling to receive anticoagulation therapy.
19. Patients who are either contraindicated or unwilling to receive anti-viral prophylaxis for prevention of Varicella reactivation.
20. Patients that do not agree to be registered in, and abide by the requirements of the i-access[®] Risk Management Program

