Skeletal Survey ^f	X				X		
Assessment of EMD if clinically indicated ^g	X				X		
B ₂ M	X	X					
LDH	X	X				X	
SPEP	X	X				X	
UPEP ^h	X	X				X	

FLC	X	X				X	
CFNA ⁱ		X		X	X	X	
BMAT ^j	X				X	X	
New primary malignancy assessment ^k		X				X	X
AE reporting	X	X				X	X
Progression data ^l							X

Abbreviations:

CR = complete response; EOT = end of treatment; FISH = fluorescent in-situ hybridization; ECOG = Eastern Cooperative Oncology Group; ECG = electrocardiogram; FBE = full blood examination; QOL = quality of life; EMD = extramedullary disease; B₂M = beta 2 microglobulin; LDH = lactate dehydrogenase; SPEP = serum protein electrophoresis; UPEP = urine protein electrophoresis; FLC = free light chain assay; CFNA = circulating free nucleic acid; BMAT = bone marrow aspirate and trephine; AE = adverse event.

^a Screening should be conducted within 28 days of starting treatment.

^b Day 15 evaluations only for cycles 1 to 3.

^c Patients who discontinue the study drug regimen for disease progression must complete the end-of-treatment (EOT) visit, which should occur within 30 days (\pm 1 week) after the last dose of study drug and before the start of subsequent antineoplastic therapy.

^d A serum pregnancy test will be performed for women of childbearing potential during screening, day 1 of each cycle and at EOT. The serum pregnancy test may be collected up to 3 days before dosing. The results must be available and negative before the study drug regimen is administered.

^e QLQ-C30 = Quality of Life Questionnaire.

^f Within 60 days of cycle 1 day 1 acceptable at screening. To be repeated at time of serological CR and otherwise only if clinically indicated.

^g For those with documented extramedullary disease, radiographic assessments should be undertaken at screening, at the time of serological CR and otherwise, only if clinically indicated. The same imaging modality used at screening (CT/PET-CT/MRI) should be used for all follow-up assessments.

^h Only to be repeated if abnormal at baseline.

ⁱ Correlative studies (peripheral blood collection)

^j BMAT will be obtained at screening, at serological CR and progression for response assessment and correlative studies.

^k New primary malignancies that occur during the follow-up period must be reported, regardless of causality to study regimen, for a minimum of three years after the last dose of the investigational product

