6.4 Excluded Concomitant Medications and Procedures

The following medications and procedures are prohibited during the study.

Systemic treatment with any of the following metabolizing enzyme inducers should be avoided, unless there is no appropriate alternative medication for the patient's use (Rationale: If there were to be a drug-drug interaction with an inducer, ixazomib exposure would be decreased:

- Strong CYP3A inducers: rifampin, rifapentine, rifabutin, carbamazepine, phenytoin, and phenobarbital

The following medicinal products and procedures are prohibited during the study.

- Excluded foods and dietary supplements include St. John's wort and Ginkgo biloba

- Any antineoplastic treatment with activity against MM, other than study drugs
- Radiation therapy (note that, in general, the requirement for local radiation therapy indicates disease progression)
- Platelet transfusions to help patients meet eligibility criteria are not allowed within 3 days prior to study drug dosing for any dosing day.

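### Eligibility sets no interval since the last systemic anti-myeloma therapy and no response baseline is named, so falls in M-protein from earlier treatment can count as ITD responses

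*Protocol*

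**What the plan says.** **Intervals that are set (Protocol 5.2).** Surgery, infection and strong CYP3A inducers each have a 14-day window. Exclusion 5 begins "Radiotherapy within 14 days before enrollment" and adds that for a small field "7 days will be considered a sufficient interval between treatment and administration". Exclusion 16 bars "Participation in other clinical trials, including those with other investigational agents not included in this trial, within 30 days of the start of this trial".

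**Prior systemic therapy (5.1 and 5.2).** Inclusion 4 asks for relapsed/refractory disease and one to three earlier therapies. Exclusion 3 requires recovery to Grade 1 toxicity or less "from the reversible effects of prior chemotherapy". Neither gives a number of days since the last dose.

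**Between screening and first dose.** Footnote a of the Schedule of Events reads "Screening should be conducted within 28 days of starting treatment". SPEP, UPEP and FLC are scheduled at screening and on Day 1 of each cycle, with UPEP repeated only if it was abnormal at baseline. Section 6.4 prohibits, during the study, "Any antineoplastic treatment with activity against MM, other than study drugs". Dexamethasone is one of the study drugs (4.1). The response criteria (11.4) are percentage reductions, and they do not say which sample is the reference.

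**Analysis (7.1, 7.1.6).** The primary efficacy analysis uses all registered patients (FAS). The major deviations that remove a patient from the Per-Protocol Set (PPS) include "a response status of MR or better at registration", incompletely documented response status at entry, and non-study cancer treatment given after registration. The list is expressly open. The PPS is a sensitivity analysis only.

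**The concern.** In a single-arm trial every response is credited to the study regimen. The exposure most able to move M-protein, the previous anti-myeloma regimen, is the one with no entry interval. The sponsor evidently saw the risk, because entering the trial already in minimal response is a listed deviation. That guard acts only on the PPS, however. It also does not reach a patient whose M-protein is falling but has not yet crossed the minimal-response threshold.

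A steroid course between screening and Cycle 1 Day 1 raises a related question. If the screening sample is the reference, the resulting fall counts toward response.

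At stake is the proof-of-concept decision. The observed response rate is judged against 60% and its posterior against a fixed 45%, with no concurrent comparator to absorb carry-over.

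**Working it through.** **Inputs from the Protocol.** n = 45 (4.2). Both criteria must hold: observed response rate of at least 60%, and posterior probability of at least 90% that the true rate exceeds 45% (7.1.1; 7.1.6 writes more than 90%, which changes nothing here). Prior Beta(0.86805, 1). Design response rate 65%, stated probability of declaring efficacy 0.80. Response means PR or better, as in 7.1.6.

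**Step 1: the decision rule.** 0.60 × 45 = 27. With x responders the posterior is Beta(0.86805 + x, 1 + 45 − x), and P(rate > 0.45) is:

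| x | Posterior probability |
|---|---|
| 24 | 0.866 |
| 25 | 0.919 |
| 27 | 0.977 |

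The posterior criterion is met from 25 responders, so the observed-rate criterion binds and efficacy is declared at x ≥ 27.

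**Step 2: reproduce the plan's figures.** P(X ≥ 27 | n = 45, p = 0.65) = 0.806, against the stated 0.80. The posterior is 0.905 at 12/20 and 0.963 at 19/31, in line with the 90% and 95% stated in 7.1.1. The sample-size arithmetic is sound.

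**Step 3: chance of declaring efficacy with no carry-over.** P(X ≥ 27 | n = 45, p = 0.45) = 0.031.

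**Step 4: a fixed number of carry-over responders (assumed).** Suppose m patients are certain to be scored as responders because of earlier treatment and the rest respond at 45%. The chance is P(Bin(45 − m, 0.45) ≥ 27 − m).

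| m | Expression | Chance |
|---|---|---|
| 1 | P(Bin(44, 0.45) ≥ 26) | 0.042 |
| 2 | P(Bin(43, 0.45) ≥ 25) | 0.058 |

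**Step 5: a carry-over rate (assumed).** If a fraction c of true non-responders is misattributed, p = 0.45 + 0.55c.

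| c | p | Expected extra responders, 45 × 0.55c | P(X ≥ 27) |
|---|---|---|---|
| 5% | 0.4775 | 1.2 | 0.067 |
| 10% | 0.505 | 2.5 | 0.130 |

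The two models agree. Two certain carry-over responders add 2 × 0.55 = 1.1 expected responses and give 0.058; the 5% rate adds 1.2 and gives 0.067.

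**The case against.** The best reply is that the eligible population leaves little room for carry-over. The Protocol Summary requires relapsed/refractory disease by IMWG criteria, so many entrants will have rising M-protein. A patient who stopped a regimen for intolerance is held back by exclusion 3, by the neuropathy exclusion and by the blood-count limits. Response categories of PR or better need two consecutive assessments (11.4), which filters out a single transient value. The 7.1 deviation list is open and can be extended before database lock. The choice of baseline sample is often left to the SAP. The 45% benchmark comes from an internal retrospective review whose own entry intervals are not described, so it may carry some of the same effect.

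Much of this stands, and it makes large carry-over rates unlikely. It does not close the gap. Neither the summary nor inclusion 4 says that progression must be documented after the last regimen, or when. Two assessments do not filter a sustained fall. A SAP can define a baseline but cannot change who is enrolled.

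A reader might infer more than the documents support on four points:

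- **That the bias can only be upward.** For falls before dosing this holds only if screening is the baseline. If Cycle 1 Day 1 is the baseline, such a fall lowers the reference and is not credited to ITD.
- **That dexamethasone before Cycle 1 is plainly permitted.** Section 6.4 can fairly be read as exempting only dexamethasone given on the protocol schedule. The text is unclear; it does not grant permission.
- **That an irradiated plasmacytoma could produce a response.** In 11.4 lesion shrinkage is required in addition to the M-protein criteria, so irradiation could at most remove a barrier to PR.
- **That 7.1 guards only against minimal response at entry.** It also names non-study cancer treatment after registration.

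**Conclusion.** The point holds as an eligibility gap. The Protocol sets no minimum interval since off-trial systemic anti-myeloma therapy, does not clearly bar steroid given for myeloma before Cycle 1 Day 1, and names no response baseline. The only safeguards against entering while still responding sit in a sensitivity set, so a patient responding to earlier treatment can enter the FAS and be counted.

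The size cannot be derived from the Protocol. Under assumed carry-over, the chance of declaring efficacy at a true 45% rises from 0.031 to 0.042 or 0.058 (one or two certain carry-over responders), or to 0.067 or 0.130 (5% or 10% of non-responders misattributed). These figures assume independent patients and a full 45 registered. They show how sensitive the rule is to one or two misattributed patients; they do not estimate what will happen. No stated figure in the Protocol is wrong on this point.

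**What to change.** 1. Add an exclusion to 5.2 for systemic anti-myeloma therapy, including corticosteroid given for myeloma, within a stated interval before Cycle 1 Day 1. The length is a clinical decision for the sponsor.
2. Name the Cycle 1 Day 1 pre-dose SPEP, UPEP and FLC as the response baseline in 11.4. The schedule already collects them. Where UPEP was normal at screening and is not repeated, say that the screening result stands.
3. Add therapy inside that interval to the major deviations in 7.1, beside the existing items on minimal response or better at registration and on other cancer treatment after registration.

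The cost is one eligibility sentence, one baseline definition and one line in the deviation list. No visit or test is added, and the sample size and decision rule do not change. The downside is that a few patients start slightly later.
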